2.5 Objectives

The primary aim of the study is to compare the effects of three types of micronutrient supplements among Ghanaian pregnant and lactating women and to assess the effect of LNS-P&L given to pregnant and lactating women and LNS-20gM provided to children from 6 to 18 mo of age on child growth and micronutrient status. We also aimed to explore what background characteristics (e.g. social, economic, demographic, health, nutritional, etc.) might modify the effects of LNS among women and their infants.

The null hypotheses were that:

a) The three groups of infants whose mothers receive the three micronutrient treatments will not differ significantly in mean birth length (crude length and length-for-age z-score), and

b) Infants whose mothers received LNS during pregnancy and lactation, and who receive LNS from 6 to 18 months of age will not differ significantly in length-for-age z-score at 18 mo from infants of the other two groups.

2.6 Blinding

The statistical analysis plan was written by study investigators, all of whom were blinded to the group assignments, until the final study results are released by the study statistician.

2.7 Efficacy outcomes

2.7.1 Primary efficacy outcomes

The study has two primary efficacy outcomes, namely:

- a) Length of baby delivered by enrolled woman measured within 48 hours of delivery, which is defined by (i) Crude length in cm, and (b) Length-for-age z-score, and
- b) Length-for-age z-score of child at 18 mo of age.

2.7.2 Secondary efficacy outcomes

Secondary outcomes include:

Maternal:

- Anthropometric status (weight, BMI, mid upper arm circumference and sub-scapular skin-fold thickness) at 36 gestational weeks (GW) and 6 mo postpartum.
- Weight of child delivered (measured within 48 hours of delivery).
- Gestational age at delivery.
- Anemia, micronutrient (iron, vitamin A, B-vitamins, zinc) and essential fatty acid status at 36 GW and 6 mo postpartum.
- Malarial antigen at 36 GW and 6 mo postpartum.
- Total plasma cholesterol at 36 GW.
- Blood pressure and urinary iodine, isoprostane (marker of oxidative stress) and 8-hydroxy-2'deoxyguanosine (8-OHdG) (marker of DNA damage) at 36 GW.
- Breast milk composition (essential fatty acids, vitamin A, B-vitamins, iodine) at 6 mo postpartum.
- Depressive symptoms at 6 mo postpartum.
- Salivary cortisol at 28 GW and 36 GW.
- Morbidity between enrollment and 36 GA and 6 mo post-partum.

Child:

- Anthropometric status (weight, length, head circumference and mid upper arm circumference) at birth and 3, 6, 12 and 18 mo.
- Anemia, micronutrient (iron, vitamin A, B-vitamins, iodine) and essential fatty acid status, and malarial antigen at 6 and 18 mo.
- Morbidity between 6 and 18 mo.
- Child feeding practices and maternal report of child sleep patterns at 6, 12 and 18 mo.
- Energy and nutrient intake from complementary foods at 9 and 15 mo.
- Antibody response to measles vaccination at 12 mo.

- Achievement of five motor milestones (sitting without support, standing alone, walking with assistance, walking alone and running) and four other developmental milestones (pronouncing single words like mama / dada, waving goodbye, eating by self, drinking from a cup) from 0 to 18 mo of age.
- Neuro-behavioral development at 18 mo of age.

2.8 Safety outcomes

We assessed safety by evaluating (a) Adverse events (b) Severe adverse events, and (c) Abnormally low anthropometric values.

2.8.1 Adverse events

i. Women

Adverse events outcomes were:

- a) Proportion of follow-up visits completed at which woman reported adverse event since last visit/during last two weeks.
- b) Proportion of days under surveillance woman had adverse event.
- c) Proportion of follow up visits completed at which woman reported adverse event on the day preceding the visit day.
- d) Number of visits to a clinic, hospital or pharmacy because of morbidity symptoms

Adverse events included the presence of the following at any follow up visit:

- Loss of appetite
- Nausea
- Vomiting
- Diarrhea
- Bloody stools
- Mucus in stool
- Fever
- Mastitis (during lactation only)
- Cough
- Sore throat
- Nasal discharge
- Pregnancy related abdominal pain (during pregnancy only)
- Pregnancy related bleeding (during pregnancy only)
- Visit to clinic, hospital or pharmacy because of morbidity symptoms

ii. Infants

Adverse events outcomes were:

- a) Incidence of mild, moderate and severe morbidity symptoms.
- b) Number of visits to a clinic, hospital or pharmacy because of morbidity symptoms.
- c) Prevalence of morbidity at 6, 12 and 18 months.

Morbidity definitions will be based on the following symptoms assessed:

- Rashes
- Reduced activity due to illness

- Poor appetite
- Poor stool consistency (semi-liquid, liquid or very liquid)
- Blood or mucus in stool pathology
- Vomiting
- Fever
- Cough
- Rapid breathing
- Difficult breathing
- Nasal discharge

2.8.2 Serious adverse events

Serious adverse events (SAE) outcomes:

- a) Number of SAEs reported, ie. if a subject has more than one occurrence of SAEs, all the SAEs will be counted.
- b) Number and proportion of subjects with SAEs i.e. if a subject has more than one occurrence of SAEs, the subject will be counted only once.

Conditions regarded as SAEs were:

- a. Death of subject.
- b. Any loss of pregnancy regardless of gestational age.
- c. Hospitalization (overnight stay in the hospital because of illness).
- d. Hemoglobin less than 5.0 g/dl (or 50 g/l).
- e. Subject extremely ill. This is used to define (a) "life-threatening conditions" (including seizures, coma, tetany, diabetic ketoacidosis, disseminated intravascular coagulation, diffuse petechiae, paralysis, acute psychosis, severe depression), (b) "persistent or significant disability / incapacity" and (c) "other serious medical condition".
- f. Congenital abnormality/ birth defect.

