3.0 Design

3.1 Sample size and power

Sample size calculations were based on being able to detect an effect size of 0.3 (difference between groups, divided by the pooled SD) for each outcome, assuming 3 groups, power of 80% and alpha=0.05. This required 216 per group, for a total of 648 subjects. Allowing for up to 25% loss to follow-up by 18 months, we needed to recruit 864 subjects. For the biochemical outcomes, we assumed an effect size of at least 0.5, which required a subsample of 79 per group, for a total of 315 subjects after allowing for attrition.

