3.2 Informed consent issues

All eligible women did sign or thumbprint informed consent for their own participation and for the participation of their babies (upon delivery) prior to being enrolled. If a participant or their parent (in the case of infants) withdraws consent (refuse to continue in the study) at any point of the study, then we will stop any study treatment or follow-up, and if the participant is a pregnant woman, we will advise her to obtain routine supplements from the antenatal clinic. Data on participants who refuse to continue in the study will be included in our analysis on the intention-to-treat basis. However, the primary outcome data for such participants, if missing, will not be imputed.

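### SAE and care-visit outcomes carry no observation time, so if retention differs between arms the counts will differ at equal true rates

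*SAP*

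**What the plan says.** SAP section 2.8.2 sets two SAE outcomes: "Number of SAEs reported, ie. if a subject has more than one occurrence of SAEs, all the SAEs will be counted", and "Number and proportion of subjects with SAEs", where a subject with several SAEs counts once. The denominator of that proportion is not stated. Section 2.8.1 lists, for women (item d) and for infants (item b), "Number of visits to a clinic, hospital or pharmacy because of morbidity symptoms".

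The other women's outcomes in section 2.8.1 are built differently. Item (a) is "Proportion of follow-up visits completed at which woman reported adverse event since last visit/during last two weeks", item (b) is "Proportion of days under surveillance woman had adverse event", and item (c) again uses completed visits. The list of conditions that count as adverse events in women includes a care visit, so items (a) to (c) cover care visits as well. Infant morbidity is given as incidence and prevalence.

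On follow-up, section 3.1 sizes the trial "Allowing for up to 25% loss to follow-up by 18 months". Section 3.2 says of a participant who withdraws consent, "then we will stop any study treatment or follow-up". Section 2.9 analyses subjects in their assigned group and uses the data of lost subjects where they exist. Sections 4.8 to 4.10 name ANCOVA, PROC GLM, FREQ, LOGISTIC, MIXED and GLIMMIX. They specify no rate model, offset or time-to-event method.

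**The concern.** A count of repeatable events grows with the time a subject is watched. A proportion of subjects affected grows with it too, though more slowly. When observation ends early for some subjects, raw figures mix the event rate with retention. The plan deals with this for women's symptoms but not for SAEs or for infants' care visits, and the women's separate visit count (d) has the same form.

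The plan gives no assurance that retention will be equal. Blinding is only partial, and only the LNS arm's infants receive a product (section 2.1). If retention does differ, the error can go two ways: an arm that keeps its participants can appear to have more SAEs, or harm in an arm that participants leave can be under-recorded.

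**Working it through.** **The plan's own figures.** A one-way ANOVA F test with three groups, an effect of 0.3 SD between the extreme groups (the third midway), alpha 0.05 and 80% power gives 216 per group (power 0.802), as stated. Then 3 × 216 = 648, 648/0.75 = 864, and 864/3 = 288 per arm. The 25% is thus an overall allowance. The SAP gives no loss by arm and no SAE or care-visit rate, so the splits and rates below are assumptions.

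**Mean observation time.** Scale the follow-up period to 1 and let L be the share lost by its end. Two loss patterns:

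- Losses spread evenly: mean time = 1 − L/2.
- Constant loss hazard: mean time = L / (−ln(1 − L)).

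With the same constant true event rate in both arms, the expected ratio of raw counts is the ratio of mean times.

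| Assumed loss, arm A vs arm B | Even spread | Constant hazard |
|---|---|---|
| 25% vs 25% | 0.875/0.875 = 1.00 | 0.869/0.869 = 1.00 |
| 20% vs 30% | 0.900/0.850 = 1.06 | 0.896/0.841 = 1.07 |
| 15% vs 35% | 0.925/0.825 = 1.12 | 0.923/0.812 = 1.14 |

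If losses fall on average a quarter of the way through, mean time is 1 − 0.75L. The ratios become 0.850/0.775 = 1.10 and 0.8875/0.7375 = 1.20.

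**Proportion of subjects affected.** Assume 0.2 SAEs per subject over full follow-up and evenly spread loss. A completer has risk 1 − e^(−0.2) = 0.181. A subject lost at a uniformly distributed time has average risk 1 − 0.181/0.2 = 0.094.

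- L = 15%: 0.85 × 0.181 + 0.15 × 0.094 = 0.168.
- L = 35%: 0.65 × 0.181 + 0.35 × 0.094 = 0.151.

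The gap is 1.7 percentage points with no true difference. Its standard error at 288 per arm is √(0.168 × 0.832/288 + 0.151 × 0.849/288) = 0.031, about 3 points.

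**If the raw counts were tested.** Take Poisson counts, 288 per arm, 20% versus 30% loss and constant loss hazard. At 0.2 events per subject the expected counts are 51.6 and 48.4, so z = 3.2/√100 = 0.32 and a nominal 5% test rejects 6.2% of the time. At 2 events per subject they are 516.3 and 484.5, z is about 1.0, and it rejects 17.1% of the time. The distortion therefore matters more for frequent events such as care visits than for rare SAEs.

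**After dividing by person-time.** The expected rate ratio is 1.00 in every row, provided loss is unrelated to risk.

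**The case against.** The main counter-argument is that numbers of SAEs and of subjects affected are customary descriptive safety output, and that the SAP names no test for them. A reader might infer that the plan compares raw counts formally. It does not say so, and the error rates above apply only if someone does. The CONSORT flow diagram promised in section 4.1 will also show losses by arm.

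Other limits stand:

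- Women's care visits already have exposure-based versions through items (a) to (c), so for women item (d) is an additional count. The gap for care visits is chiefly in infants.
- The 25% refers to 18 months, the child endpoint. Section 4.7 ends women's morbidity follow-up at about 6 months postpartum, so losses of that size should not be carried over to women.
- Pregnancy loss and congenital abnormality arise in pregnancy or at birth and depend little on later retention. The low-haemoglobin SAE depends on blood being measured, which is scheduled at set times. The ratios above overstate the effect for all of these.
- It is tempting to say that early leavers count as event-free throughout. They do not: SAEs before leaving are counted, and a loss through death is itself an SAE. Only their unobserved time is at issue.
- At 0.2 SAEs per subject, even the 15% versus 35% split shifts the proportion by only about half a standard error.

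These points narrow the concern without removing it. The flow diagram shows how many left, not how long each subject was observed. Sections 4.10 and 4.12 promise later SAP updates for secondary outcomes, but SAEs are defined in section 2.8 and are not in that list, so the promise does not clearly reach them.

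**Conclusion.** The point holds as a conditional weakness. The SAE outcomes and the care-visit counts are defined without observation time in a plan that expects loss, ends follow-up at withdrawal, and uses exposure denominators for other outcomes in the same section. If retention differs between arms, raw counts of events spread evenly over follow-up are off by about 6% to 7% at 20% versus 30% loss and 12% to 14% at 15% versus 35%. They are off by more if losses come early and by nothing if loss is equal.

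A reader might conclude that the better-retained arm will look less safe. The documents do not support that: they give no loss by arm and no evidence that retention will differ. The size rests on the assumed splits, a constant event rate and loss unrelated to risk. It is modest for the proportion with an SAE and larger for frequent counts. The change is worth making because retention by arm is unknown when the plan is written, and observation time should be defined before results are seen.

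**What to change.** In section 2.8.2, and in section 2.8.1 women (d) and infants (b):

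- Keep the raw counts and proportions as descriptive output, and state the denominator of the SAE proportion.
- Report observation time by arm: for women from randomisation, for infants from birth, to the last completed visit, death or withdrawal.
- Analyse repeatable SAEs (such as hospitalisation) and care visits, chiefly in infants, as rates per person-time. Use a log-link count model (for example negative binomial) with log observation time as offset.
- For subjects affected, use time to first SAE.
- For pregnancy loss and congenital abnormality, use pregnancies or births as the denominator, since person-time does not suit once-only events.

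The cost is SAP wording and some extra programming. The fortnightly maternal and weekly infant visits in section 4.7 should supply the person-time, so no new data collection is needed. The rates remain unbiased only if loss is unrelated to risk; dropout caused by harm is not cured by an offset, and the report should say so.

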3.5 Interim data analysis

For each of the study outcome measures, we will not perform any interim analysis during the period primary data collection is ongoing. That is, for each outcome variable, analysis will be done only at the end of the data collection for that outcome. However the Data and Safety Monitoring Board (DSMB) and Institutional Review Board (IRB) can request interim analysis of

morbidity and all-cause mortality, by treatment group. In case of any evidence of a difference between treatment groups in morbidity and/ or all-cause mortality, DSMB will inform the Study Management Team and advise the appropriate course of action.

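### SAE outcomes are not defined by type and the denominator is not stated, so a difference between arms in pregnancy loss or birth defects could be obscured by other SAEs

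*SAP*

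**What the plan says.** SAP section 2.8.2 names two SAE outcomes. The first is "Number of SAEs reported, ie. if a subject has more than one occurrence of SAEs, all the SAEs will be counted". The second is "Number and proportion of subjects with SAEs i.e. if a subject has more than one occurrence of SAEs", that subject adds one and no more.

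One lettered list of qualifying conditions serves both. It includes "Death of subject", "Any loss of pregnancy regardless of gestational age", "Hospitalization (overnight stay in the hospital because of illness" and "Congenital abnormality/ birth defect", together with hemoglobin under 5.0 g/dl and a category for extreme illness. No outcome is attached to any single condition.

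Section 2.8.1 sets out non-serious adverse events under separate headings for women and for infants. Section 2.8.2 makes no such division and speaks only of subjects.

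Elsewhere, section 3.5 allows the Data and Safety Monitoring Board (DSMB) or the Institutional Review Board (IRB) to ask for an interim analysis of "morbidity and all-cause mortality, by treatment group". The secondary outcomes in 2.7.2 and the shells for Tables 2 to 4 include neither pregnancy loss nor birth defect nor death. There is no SAE table shell.

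**The concern.** The supplements are taken from 20 weeks of gestation or earlier until delivery, so pregnancy loss and birth defects are among the harms a reader will want compared by arm. Under 2.8.2 they enter only as part of a total. If other SAEs occur at similar rates in all arms, they add variance to the any-SAE proportion. They also shrink the difference, because some women who lose a pregnancy would already count through another event. The trial could then report similar SAE proportions while one type differs between arms.

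The undefined denominator is a second problem. The list holds one event that only a pregnant woman can have (loss) and one that is recorded in offspring (birth defect). A proportion of subjects could be taken over women, over infants or over both, and these are different quantities. The SAP does not fix which one will be reported.

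**Working it through.** **Does another part of the SAP supply the comparison?**

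| Place in SAP | What it offers | Final comparison by arm of loss or birth defect? |
|---|---|---|
| 2.7.2 secondary outcomes | Birth weight, gestational age, growth, morbidity and others | No |
| 2.8.1 adverse events | Symptoms and care-seeking, women and infants separate | No; pregnancy-related bleeding is listed, loss is not |
| 2.8.2 SAEs | Total SAEs; subjects with any SAE | Only inside the total |
| 3.5 interim | Morbidity and all-cause mortality, on request | No; optional, interim, names neither |
| 4.1 flow chart | CONSORT diagram | May show losses as reasons for leaving; not a comparison |
| Tables 2 to 4 | Birth and 18-month measures | No |

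**Sample size per arm.** Section 3.1 states 216 per group, 648 in all, and 864 recruited. A one-way ANOVA F test with three groups, a largest difference of 0.3 SD and the third mean midway has f = √(2 × 0.15² / 3) = 0.1225. At alpha 0.05 and 80% power this needs 215.1, so 216 per group. Then 648 / (1 − 0.25) = 864, and 864 / 3 = 288 women per arm. The stated size reproduces and is used here only to obtain n.

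**Illustration of the dilution.** Inputs:
- From the SAP: n = 288 per arm (3.1); two-sided 5% tests (2.9).
- Assumed, because the SAP gives no SAE rate: pregnancy loss p of 3% against 8%; other SAEs at rate h, equal in both arms and independent of loss, with h from 5% to 30%.

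Risk of any SAE: P = 1 − (1 − p)(1 − h). The difference between arms becomes (p₂ − p₁)(1 − h).

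Power = Φ[(d − 1.96·se₀) / se₁], where d = P₂ − P₁, se₀ = √(2·P̄(1 − P̄)/n), P̄ is the mean of the two risks, and se₁ = √(P₁(1 − P₁)/n + P₂(1 − P₂)/n).

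Loss alone: d = 0.05, P̄ = 0.055, se₀ = 0.0190, se₁ = 0.0189. The argument is 0.676, so power is 75%.

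Any SAE with h = 20%: P₁ = 0.224, P₂ = 0.264, d = 0.040, se₀ = 0.0358, se₁ = 0.0358. The argument is −0.843, so power is 20%.

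| Assumed risks | Alone | h = 5% | h = 10% | h = 20% | h = 30% |
|---|---|---|---|---|---|
| Loss 3% vs 8% | 75% | 47% | 33% | 20% | 14% |
| Loss 3% vs 6% | 41% | 22% | 15% | 10% | 8% |
| Loss 3% vs 9% | 86% | 60% | 43% | 27% | 18% |
| Birth defect 1% vs 5% | 81% | 40% | 25% | 15% | 11% |

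The birth-defect row keeps n = 288; births will be fewer than enrolled women, so its powers are somewhat high. For an event at 1% against 2%, power is about 17% even when analysed alone.

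**Three arms.** Section 4.8 begins with a global three-group test. A simulated three-group chi-square test with risks of 3%, 3% and 9% gave 92% power for loss alone, and 45%, 27% and 18% as any SAE with h at 10%, 20% and 30%. The pattern does not depend on the two-arm simplification.

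**The case against.** The strongest reply is that 2.8.2 defines outcomes and lists six lettered conditions without forbidding a tabulation by condition. It gives no SAE test or model, and event listings are commonly left to the protocol, which is not shown. This stands in part: a reader might infer that SAEs will be analysed only in pooled form, and the text does not go that far. What it shows is that no outcome by type is specified.

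Other stronger readings also lack support:

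- **Women and infants pooled.** A reader might infer this from the undivided word for subjects. It is not stated, and the split in 2.8.1 makes separate reporting a possible reading. What can be said is that the denominator is undefined.
- **Routine hospital stays swamping the rest.** Only overnight stays because of illness qualify, so ordinary delivery stays do not count.
- **Pregnancy loss and birth defects as the least frequent SAEs.** The SAP gives no rates, and very low hemoglobin or extreme illness could be rarer.
- **Lost infant follow-up offsetting extra pregnancy losses.** This is conceivable if women and infants share a denominator, but nothing in the SAP establishes it and it has not been computed.
- **Deaths wholly hidden.** Section 3.5 gives mortality by arm a route, though an optional and interim one.

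It is also fair to say that the power contrast rests on assumed and fairly large effects. For very rare events, reporting by type improves transparency more than detection.

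**Conclusion.** The point holds in this limited form. Section 2.8.2 fixes two SAE outcomes over a mixed list, does not define whose proportion is reported, and no other section defines a final between-arm outcome for pregnancy loss, birth defect or death. Followed as written, the plan makes a diluted comparison of these harms.

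The direction of the dilution follows from adding an equal, independent background of other SAEs. Its size rests entirely on assumed rates: in the central example power falls from about three in four to between about one in two and one in seven. These figures illustrate and do not predict. The matter is one of safety analysis and reporting, not clinical management. It should be corrected, but it does not affect the primary outcomes.

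**What to change.** In SAP 2.8.2, define SAE outcomes separately for women and infants and by type, with denominators stated:

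- pregnancy loss per enrolled pregnancy;
- maternal death per enrolled woman;
- infant death and congenital abnormality, each per infant born;
- hospitalisation, separately for women and for infants;
- the remaining listed conditions, likewise by type.

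Give each by arm with a risk difference and an exact 95% confidence interval, and add a table shell. Keep the total count and the any-SAE proportion as a summary line, stating for the proportion which subjects form the denominator.

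The cost is SAP wording and a longer table, with wide intervals for rare types. It should need no new data if the SAE forms record the condition; the appendices listing the forms are not available here to confirm that.
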